11.3.2. Response

The measure of response and progression will be determined by the local investigator according to the RANO criteria (Wen, 2010). All treatment decisions should be based on the RANO criteria as assessed by the local investigator.

Target lesions are measured in their two largest perpendicular diameters. Their area is conventionally calculated as the product of these diameters. In case of multifocal disease with more than one target lesion, the total tumor size is calculated as the sum of the area of all target lesions.

Response is defined as follows according to the RANO criteria, which also consider T2 weighted and FLAIR images:

- Complete response (CR) requires all of the following: 1) Complete disappearance of all enhancing measurable and non-measurable disease; 2) No new lesions; 3) Stable or improved non-enhancing abnormalities on FLAIR/T2 images as compared to baseline; 4) Patients must be off corticosteroids (or on physiologic replacement doses only) and stable or improved clinically.
- Partial response (PR) requires all of the following: 1) Only reductions of cross-sectional areas of 50% or more in the sum of product of perpendicular diameters of target lesions will be considered a response; when calculating the response, the baseline magnetic resonance imaging (MRI) must be used for comparison ; 2) No progression of non-target lesions; 3) No new lesions; 4) Stable or improved non-enhancing abnormalities on FLAIR/T2 images as compared to baseline; 5) Patients should be on a corticosteroid dose that should not be greater than the dose at time of baseline scan, and should be stable or improved clinically.
- Progressive disease (PD):
 - Progression is defined by any of the following: 1) 25% increase in sum of the products of perpendicular diameters of enhancing lesions (compared with baseline if no decrease) on stable or increasing doses of corticosteroids; 2) a significant increase in T2/FLAIR non-enhancing lesions on stable or increasing doses of corticosteroids compared with baseline scan or best response after initiation of therapy, not due to comorbid events; 3) the appearance of any new lesions; 4) clear progression of non-measurable lesions; or 5) definite clinical deterioration not attributable to other causes apart from the tumor, or to decrease in corticosteroid dose. Failure to return for evaluation as a result of death or deteriorating condition should also be considered as progression.
 - If the evidence of PD is equivocal (target or non-target), treatment may continue until the next assessment, but if PD is confirmed at the next follow-up, the earlier date must be used as the date of progression
 - For patients operated at recurrence and without measurable or non-measurable disease after surgery, any new appearance of tumor will qualify for PD. In case non-measurable tumor is left after surgery, i.e. tumor less than 10 mm, unequivocal progression of non-target disease may be accepted as evidence of disease progression, where the overall tumor burden has increased sufficiently to merit discontinuation of treatment. Modest increase in the size of a non-target lesion is not considered unequivocal progression. If the evidence of PD is equivocal (target or non-target), treatment may continue until the

next assessment, but if confirmed, the earlier date must be used as the date of progression. This implies that in case of gross total resection of the enhancing lesion, if at follow up minimal enhancement of unclear significance arises, treatment may continue until further follow-up gives unequivocal evidence of tumor progression.

- **Stable Disease:** This occurs if the patients did not qualify for CR, PR, or progression (see above) and requires: 1) No meaningful change in the appearance of the FLAIR/T2 images compared to baseline or to the nadir (point with the smallest FLAIR/T2 abnormalities) if a decrease occurred. 2) The patient should be stable clinically. In the event the steroid dosage has been increased for new signs and symptoms without confirmation of disease progression on imaging, and further follow-up imaging shows that with hindsight this increase in steroids was indeed unequivocally needed due to disease progression, the date of progression will be the date steroids were increased.
- In this protocol, although the primary endpoint is OS, in view of the relevance of objective responses, PR, CR, and equivocal PD need to be confirmed with an extra MRI made 4 weeks later.

Criterion	CR	PR	SD	PD
T1 gadolinium enhancing disease	None	≥ 50% ↓	<50% ↓ but <25% ↑	≥ 25% ↑
T2/FLAIR	Stable or ↓	Stable or ↓	Stable or ↓	↑
New lesion	None	None	None	Present
Corticosteroids	None	Stable or ↓	Stable or ↓	Not applicable*
Clinical status	Stable or ↑	Stable or ↑	Stable or ↑	↓
Requirements for response	All	All	All	Any

CR = complete response; PD = progressive disease; PR = partial response; SD = stable disease

*increase in steroids alone does not qualify for PD

The overall response is evaluated at each assessment of the disease according to RANO criteria. Best overall response is the best response designation recorded from the date of randomization until disease progression. Objective/complete response includes best overall responses CR and PR/ CR only. For responders, duration of objective response (CR/PR) and CR will be measured similarly to PFS (see section 11.3.1) but starting from the time measurement criteria for CR/PR or CR (whichever is recorded first) is met. The best overall response will be presented in contingency table with frequencies and percentages. The objective response (ORR: CR/PR) and CR rates will be reported with exact (binomial) two-sided 95% CI and compared between the treatment arm over the control arm using a one-sided Cochran-Mantel-Haenszel (CMH) test, stratified by stratification factors assessed at randomization (except institution). Odds ratios will be presented with 95% CIs.

The medians of objective response (PR/CR) and CR duration will be estimated from the Kaplan-Meier curves. The Reflected Method will provide two-sided 95% CI.

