### 5.6.3 Prohibited therapies

The following treatments are NOT permitted during the study treatment:

- Treatment with other systemic anti-cancer agents before disease progression (chemotherapy, immunotherapy, anti-tumor vaccines, targeted agents, or other treatments not part of protocol-specified anti-cancer therapy)
- Concurrent investigational agents of any type before disease progression
- Craniotomy, intra-tumoral interstitial therapy, any surgical procedures under investigation or any form of radiosurgery

Any of the above will lead to patient's discontinuation from study treatment.

Additional treatment with tumor treating fields in the adjuvant setting is discouraged but will not constitute a protocol violation.

Alternative therapies are discouraged and must be discussed with the local investigator.

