## 7.1.3 Progression Free Survival

Progression Free Survival (PFS): PFS is defined as the number of days from date of randomization to the date of earliest disease progression based on Response Assessment in Neuro Oncology (RANO) criteria (as determined by the Investigator) or to the date of death due to any cause, if disease progression does not occur. Patients for whom neither death nor progression have been documented will be censored on the date of the last radiological assessment that the patient was progression-free. If a patient with no post-baseline radiological assessment then the data will be censored at the date of randomization. Patients with two or more missing response assessments prior to a visit with documented disease progression (or death) will be censored at the last visit where the patient was documented to be progression free. Patients who received new anti-cancer therapy or cancer-related surgery prior to progression or death will not be censored at the last assessment where the patient was documented as progression free prior to the new anti-cancer therapy or cancer-related surgery. Detailed censoring rules will be documented in the SAP.

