### 7.1.4.3 Response duration

For responders, duration of objective response (CR/PR) and complete response (CR) will be measured similarly to PFS (see section 7.1.3) but starting from the time measurement criteria for CR/PR or CR (whichever is recorded first) is met

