11.3.1. Progression-free Survival

Progression-free survival will be defined as the number of days from date of randomization to the date of earliest disease progression based on Response Assessment in Neuro-Oncology (RANO) criteria (as determined by the Investigator) or to the date of death due to any cause, if disease progression did not occur (the date of progression or death or censoring - date of randomization + 1). Subjects for whom neither death nor progression have been documented will be censored at the date of the last radiological assessment that the subject was progression-free. If a subject has no post-baseline radiological assessment, then the data will be censored at the date of randomization.

Subjects with two or more missing assessments prior to a visit with documented disease progression (or death) will be censored at the last assessment where the subject was documented to be progression free. Subjects who received new anti-cancer therapy or cancer-related surgery prior to progression or death will not be censored at the last assessment where the patient was documented as progression free prior to the new anti-cancer therapy or cancer-related surgery. Censoring rules are documented in section 15.2.

The following PFS analyses will be performed at 2-sided significance level $\alpha=0.05$ for exploratory purpose. The stratified LogRank test will be applied on the PFS time to test for differences between the 2 treatment groups. The Cox's proportional hazards model stratified by the stratification factors assessed at randomization (except institution) will provide the HR (including 95% CI). Summary of associated statistics for each treatment arm (median PFS time, 6-, 12-, 18-, 24-month PFS rate estimates and estimates for every 6 months thereafter as applicable) will be displayed with 95% CI computed using the same methods as for OS, and the Kaplan-Meier curve for PFS will be presented.

Progression-free survival Kaplan-Meier estimates will be calculated and unstratified Cox's proportional hazards model will be fitted for each subgroup defined in Section 11.5 in the ITT population only. Forest Plot will be displayed with a subgroup by treatment interaction test.

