15.2. Censoring Rules for PFS

Situation	Date of Progression or Censoring	Situation/Outcome
No baseline assessments and alive after 2 scheduled assessments	Randomization	Censored
Death within the first two scheduled assessments without any adequate assessment	Date of death	Event
Death between adequate assessments	Date of death	Event
No progression	Date of last adequate assessment with evidence of no progression	Censored
Study discontinuation for reasons other than disease progression or death	Date of last adequate assessment with evidence of no progression	Censored
New anti-cancer therapy or cancer-related surgery prior to progression or death	Date of last adequate assessment after start of new anti-cancer therapy or cancer-related surgery with evidence of progression prior	Event
	Date of last adequate assessment after start of new anti-cancer therapy or cancer-related surgery with evidence of no progression	Censored
Death or progression after an extended lost-to-follow-up time (two or more missed scheduled assessments)	Date of last adequate assessment with evidence of no progression	Censored

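### Best overall response has no cut-off at new anti-cancer therapy or surgery, so a response first reached after off-protocol treatment would count for the randomised arm

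*SAP*

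**What the plan says.** **Response window.** SAP 11.3.2, matching Protocol 7.1.4.1, states: "Best overall response is the best response designation recorded from the date of randomization until disease progression". The rates follow from this: "Objective/complete response includes best overall responses CR and PR/ CR only". The SAP compares ORR and CR rate between arms with a stratified Cochran-Mantel-Haenszel test and odds ratios. PR is measured against the baseline MRI, and CR and PR need a repeat MRI 4 weeks later.

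**Duration.** Protocol 7.1.4.3 states: "duration of objective response (CR/PR) and complete response (CR) will be measured similarly to PFS". SAP 11.3.2 says the same.

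**PFS.** SAP 11.3.1 states: "Subjects who received new anti-cancer therapy or cancer-related surgery prior to progression or death will not be censored at the last assessment", and Protocol 7.1.3 agrees. The censoring table in SAP 15.2 uses scans taken after the new treatment begins: "Date of last adequate assessment after start of new anti-cancer therapy or cancer-related surgery with evidence of no progression".

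**Off-protocol treatment.** Protocol 5.6.3 bars other systemic anti-cancer agents before progression and, during study treatment, "Craniotomy, intra-tumoral interstitial therapy, any surgical procedures under investigation or any form of radiosurgery". The stated consequence is that study treatment ends. Adjuvant tumor treating fields are discouraged but are not a violation.

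**Scan collection.** Protocol 5.3 covers patients who stop treatment for a reason other than progression. It continues tumour assessment, where possible, until progression or a new treatment regimen. Protocol 6.3.2.1, footnote p of the 6.4 table and 7.1.1.3 continue scans until progression, with no mention of a new regimen.

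**The concern.** SAP 4.2 asks how tumours respond to marizomib plus standard treatment compared with standard treatment alone. A response rate is normally read as activity of the regimen given. If a patient has residual enhancing tumour resected off-protocol, or starts another agent before progression, a later scan may meet CR or PR against the original baseline MRI. Under the written window that patient becomes a responder for the randomised arm.

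At stake are the ORR, the CR rate and their between-arm odds ratios. If off-protocol treatment before progression is equally common in both arms, both rates are too high. If it differs by arm, the comparison is distorted as well.

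**Working it through.** The documents give no expected ORR, no power for response and no rate of new therapy before progression. There is no stated figure to reproduce, so the main check is textual.

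**Step 1: does any rule close the window at new therapy?**

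| Candidate safeguard | What it does | Closes the response window? |
|---|---|---|
| Protocol 5.6.3, prohibited therapies | Ends study treatment | No; the patient stays in follow-up |
| Protocol 5.3 | May end scan collection at a new regimen | No; it is a collection rule, not an analysis cut |
| SAP 11.3.2, repeat MRI at 4 weeks | Confirms the finding persists | No; it does not identify the cause |
| SAP 11.3.2, patients operated at recurrence | Defines progression after surgery | No; it sets no new baseline for response |
| Per-protocol analysis | Run only if more than 10% of an arm is excluded | No; SAP 11 limits it to OS and PFS, while SAP 11.4 covers all efficacy analyses |

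**Step 2: can such scans exist?** Protocol 6.3.2.1 collects both MRI results and subsequent anti-GBM regimens in patients without progression, and SAP 15.2 has a row for them. Protocol 5.3 points the other way for patients who stopped for other reasons. It does not say whether surgery counts as a new regimen. Scans after new therapy may therefore be available for some patients and not others, and the response rule counts whichever exist.

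**Step 3: how large could it be?** All rates here are assumptions. Let p be the true ORR, s the share starting non-protocol treatment before progression, and f the share of those not already responders who are then read as confirmed CR or PR. Existing responders cannot be added twice, so:

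observed ORR = p + (1 − p) × s × f

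Take p from 10% to 20%, s from 5% to 15% and f from 25% to 50%.

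- Smallest excess: 0.80 × 0.05 × 0.25 = 0.010, or 1.0 percentage point.
- Largest excess: 0.90 × 0.15 × 0.50 = 0.0675, or about 6.8 percentage points.

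**Step 4: effect on the comparison.** Keep the true ORR equal in both arms, with p = 10% and f = 50%.

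- s = 5% in both arms: ORR is 0.10 + 0.90 × 0.05 × 0.50 = 12.25% in each, and the odds ratio is 1.00.
- s = 10% with marizomib and 5% in control: 0.10 + 0.90 × 0.10 × 0.50 = 14.5% against 12.25%. The odds ratio is (0.145/0.855) / (0.1225/0.8775) = 1.215.
- s = 5% with marizomib and 10% in control: the odds ratio is 0.823.

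The chance of a significant one-sided result was approximated as 1 − Φ[(1.96 × SE0 − d)/SE1]. Here d is the difference in observed rates, SE0 the pooled and SE1 the unpooled standard error, with no stratification. The one-sided 2.5% level is assumed, because SAP 11.3.2 gives none for this test. With an assumed 150 evaluable patients per arm, d = 0.0225, SE0 = 0.0393 and SE1 = 0.0393. The result is 8.3% when marizomib has the higher s and 0.6% when control does, against the nominal 2.5%. With 250 per arm the figures are 11.1% and 0.35%.

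**The case against.** **The situation should be uncommon.** Other agents are barred before progression. Progression is broad under RANO: it includes new lesions, T2/FLAIR increase and clinical deterioration, and a confirmed equivocal progression takes the earlier date. Much salvage treatment will therefore start after the window has closed. Protocol 7.1.1.2 adds that post-operative enhancement can persist for months, so a CR after craniotomy is not easily read. This stands as a limit on size. It does not supply the missing rule, and it says less about PR or about systemic therapy.

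**Protocol 5.3 already stops assessment.** This is the strongest textual reply. It stands in part, but other sections continue scans to progression and SAP 15.2 uses them.

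**The plan is consistently treatment-policy.** Efficacy is analysed by ITT, PFS is deliberately followed through new therapy, and duration is deliberately tied to PFS. This stands for PFS. It also stands for the duration of responses reached before new therapy, where censoring could itself be informative. It is weaker for the response rate, because the SAP 4.2 objective concerns the regimen.

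**A stronger reading on direction.** A reader might infer that the rule favours marizomib, because toxicity or the IDMC recommendation took those patients off treatment. The documents do not support this. Stopping marizomib is not starting new therapy, since under Protocol 5.3 the other drug continues alone. The primary analysis keeps the 28 April 2020 cutoff and the IDMC met on 14 September 2020, so stops prompted by that meeting can enter only the descriptive long-term follow-up analysis.

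**Conclusion.** The point holds as a gap in the definition of best overall response, and so of ORR and CR rate. Followed as written, the rule would credit a confirmed response first reached after off-protocol treatment to the randomised arm whenever such a scan exists. The documents do not show that this happened or how often.

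The excess of 1.0 to 6.8 percentage points in an arm is an illustration. It rests on the assumed p, s and f, and on new therapy being unrelated to earlier response. The direction of any between-arm bias is unknown.

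A reader might also multiply assumed rates by 375 patients per arm to count false responders. That denominator is wrong: Protocol 7.1.1 restricts objective response to patients with measurable disease, and their number is not given. Nor do the documents support calling the PFS rule an error.

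Response is listed among the other secondary endpoints in SAP 5.2.2 and is exploratory under SAP 11.1. OS and its error control are untouched. The change is worth making, but it does not affect the trial's main conclusion.

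**What to change.** 1. In SAP 11.3.2 and Protocol 7.1.4.1, define best overall response, and so ORR and CR rate, on assessments from randomisation to the earlier of progression and the start of the first non-protocol anti-cancer therapy or cancer-related surgery.
2. State whether adjuvant tumor treating fields count as such therapy for this definition.
3. Keep the current to-progression window as a sensitivity analysis.
4. Reconcile Protocol 5.3 with Protocol 6.3.2.1, footnote p of the 6.4 table, Protocol 7.1.1.3 and SAP 15.2 on whether tumour assessment continues after a new regimen.
5. Leave the PFS rule unchanged. For patients who responded before new therapy, keep the PFS-like duration rule, and add censoring at new therapy as a sensitivity analysis only.

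The updated SAP that Protocol 8.4 foresees for the follow-up analysis is a natural place. The cost is wording and one derived date, since subsequent anti-GBM regimens are already collected. ORR may be slightly lower. If response results already exist under the current rule, the revised definition should be labelled as a later change and both sets reported.

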### 7.1.4.2 Objective/complete response

Objective/complete response includes best overall responses CR and PR/ CR only. All responses must be confirmed by repeat MRI 4 weeks later.

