PD	Progressive disease
PFS	Progression-free survival
PK	Pharmacokinetics
PO	Orally (per os)
PP	Per Protocol Population
PT	Preferred term

QLQ-BN20	Quality of Life Questionnaire Brain Cancer Module
QLQ-C30	Quality of Life Questionnaire C30
QoL	Quality of life
RANO	Response Assessment in Neuro-Oncology
RT	Radiotherapy
SAE	Serious adverse event
SAP	Statistical analysis plan
SE	Standard error
SGOT	Serum glutamic oxaloacetic transaminase (AST)
SGPT	Serum glutamic pyruvic transaminase (ALT)
SP	Safety population
SSC	Study Steering Committee
TMZ	Temozolomide
TR	Translational Research
TTE	Time to event
TTF	Tumor treating fields
uMGMT	Unmethylated MGMT
ULN	Upper limit of normal
US	United States
UV	Ultraviolet
WHO	World Health Organization

2. Introduction

The intergroup Study (EORTC-1709-BTG) protocol v7.0 which was issued on 22 OCT 2019 planned a review of study data by the Independent Data Monitoring Committee (IDMC) for futility and safety. The clinical cutoff date for this analysis was 28 APR 2020 when 88 deaths were initially observed as requested by study design. After data update and cleaning, the database was locked on 07 AUG 2020. The IDMC performed the study review on 14 SEP 2020. At the cutoff date, 616 patients were randomized and 106 deaths were reported. Although the trial results did not cross the pre-specified futility boundary, the IDMC observed that there was as yet no evidence that marizomib provides a benefit in survival. The statistical data presented also suggested that it was extremely unlikely that a difference would emerge with additional patients or further follow-up. The IDMC observed that marizomib in this combination induced severe neurological and neuropsychiatric disorders, as well as other treatment-related Grade 3-4 side effects, in a substantial proportion of the patients. The IDMC therefore recommended that the study be discontinued from further recruitment and that results be disclosed to the medical community as soon as possible. However, if patients still on treatment were tolerating marizomib, they were allowed to continue, if so wished by the patient and treating physician. The IDMC did not request that a further interim analysis be implemented.

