Following the IDMC recommendation, the patient recruitment was prematurely closed. The total number of randomized patients was 749 (750 planned). The results of the study were prematurely disclosed to the study investigators and to Celgene, a BMS company, and Bristol Myers Squibb (BMS). An amended study protocol v8.0 was released on 30 SEP 2020 to reflect that the interim OS analysis performed is considered as the primary OS analysis of the study.

For the publication of the primary analysis results, a new database lock will be performed in mid 2021 at the same cut-off date (28 APR 2020) as for the IDMC review but with cleaner data for, primary endpoint, study treatment exposure, safety and other secondary endpoints.

All randomized patients will be followed till the total number of overall survival (OS) events for the initially planned final analysis is observed (488 deaths in the intent-to-treat [ITT] population and 320 in the unmethylated O-6-methylguanine-DNA methyltransferase [MGMT] subgroup). The cutoff date of the long term follow-up analysis is expected Q2 2022. The number of deaths will be closely monitored, ie, every three months. More frequent monitoring might be decided when number of deaths in the ITT population gets closer to 488. At that date, a long term follow-up analysis will be performed with more mature data for all endpoints. As the primary results will have been already released, the intent of this long term follow-up analysis is for descriptive purposes only.

The original signed statistical analysis plan (SAP) should be amended and signed to describe the analyses and data presentations for the current primary analysis and the long-term follow-up analysis.

The purpose of SAP v2.0 is to ensure the credibility of the study findings by pre-specifying the statistical approaches to the analysis of study data prior to database lock. The SAP was prepared by European Organisation for the Research and Treatment of Cancer (EORTC) and reviewed by BMS. It contains definitions of analysis populations, derived variables and statistical methods for the analysis of efficacy and safety. It describes analysis conventions to guide the statistical programming work. Throughout this SAP, the treatment arms are referred to as control and MRZ.

This SAP was finalized and signed prior to the clinical database lock for the primary analysis. All statistical analyses detailed in this SAP will be conducted using SAS[®] Version 9.4 or higher.

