- ^j For WOCBP, urine or serum pregnancy tests are to be done within 7 days of randomization and within 72 hours of treatment start
- ^k If baseline assessments have been done within 14 days of start of treatment, they do not have to be repeated for cycle 1 day 1
- ^l The first MRI scan should occur 4 weeks post end of RT; the 8-week imaging schedule will start after this scan
- ^m Brain MRI scan if one has not been done in the previous 4 weeks and no progression as yet been recorded
- ⁿ At disease progression
- ^o Frozen tissue sample will be collected at progression if the patient undergoes salvage surgery
- ^p Results of MRI scans done as part of standard of care will be collected, or done as per the study schedule of every 8 weeks (continuing on initial schedule) until disease progression
- ^q For all centers, MMSE every 16 weeks \pm 1 week until disease progression;
For participating centers, tests of objective neurocognitive function: HVLT-R, Trail Making Tests Part A & B and COWA and the MOS questionnaire on self-perceived neurocognitive function every 12 weeks \pm 2 weeks, until disease progression
- ^r Quality of life assessment (modified EORTC QLQ C30/BN20) every 16 weeks \pm 1 week until death or lost to follow up
- ^s G8 will be measured in all patients aged 70 years and above at baseline.[†]
- [†] For subjects on the marizomib arm, 12-lead ECG to be collected on following days and timepoints ONLY: at baseline within 7 days of randomization: on D1 of concomitant treatment within 15 minutes after end of MRZ infusion; on Cycle 2 Day 1 of adjuvant treatment after end of MRZ infusion; and as clinically indicated.

Marizomib (NPI-0052)

Statistical Analysis Plan v2.0. Protocol 1709-BTG

EORTC

^u For subjects enrolled prior to the implementation of protocol version 5., 12-lead ECG on Day 1 on the subsequent two cycles of adjuvant treatment within 15 minutes after end of MRZ infusion.

^v In marizomib arm only : C1D1 (first day of first adjuvant cycle) 2 mL within 10 minutes after end of infusion and 2 mL at 45 minutes following end of infusion. C1D8 2mL at 45 minutes following end of infusion.

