11.3. Analyses of Secondary Efficacy Endpoints

The secondary efficacy endpoints will be analyzed based on ITT population and by MGMT methylation status.

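### At the 28 April 2020 cut-off roughly 14 to 19% of the 616 randomised patients are too recent for a confirmed response on scheduled scans, yet they stay in the ORR and CR denominators

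*SAP*

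**What the plan says.** SAP 2 keeps the interim cut-off for the primary analysis: "a new database lock will be performed in mid 2021 at the same cut-off date (28 APR 2020) as for the IDMC review". It also gives the state of the trial on that date: "At the cutoff date, 616 patients were randomized and 106 deaths were reported". Recruitment later closed at 749. SAP 3 puts the whole efficacy section in the primary report and again in the long-term follow-up report.

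SAP 11.3 sets the population for response: "The secondary efficacy endpoints will be analyzed based on ITT population and by MGMT methylation status". Under SAP 6.2.1, ITT means every randomised subject. SAP 11.3.2 then treats ORR and CR as binomial proportions: "The objective response (ORR: CR/PR) and CR rates will be reported with exact (binomial) two-sided 95% CI". It adds a stratified Cochran-Mantel-Haenszel (CMH) test and odds ratios.

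On confirmation, SAP 11.3.2 says "PR, CR, and equivocal PD need to be confirmed with an extra MRI made 4 weeks later", and Protocol 7.1.4.2 agrees: "All responses must be confirmed by repeat MRI 4 weeks later". Footnote l of the SAP 5.1 schedule fixes the start of imaging: "The first MRI scan should occur 4 weeks post end of RT".

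SAP 11.3.2 has no minimum follow-up for the response analysis, no rule for patients without a post-baseline scan, and no category for patients not yet assessable.

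**The concern.** OS and PFS deal with short follow-up by censoring. A binomial proportion does not. A patient randomised a few weeks before the cut-off adds one to the denominator and, on the scheduled scans, cannot add one to the numerator.

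The primary report is the basis for publication, so the absolute response rates per arm would be published too low. The long-term report would then show higher rates, in part only because these patients had matured, and a reader could not tell how much of the change came from that.

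**Working it through.** **The plan's own accrual figure.** Protocol 8.1.1 plans 150 patients in year 1 and 400 per year after that. At 20 months this gives 150 + (8/12) × 400 = 417. Protocol 8.3 states about 406 at approximately 20 months; 406 is reached at 12 + (256/400) × 12 = 19.7 months. The accrual model agrees with the plan.

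**Time to a confirmed response on scheduled scans.**
- Randomisation to treatment start: 0 to 1 week (Protocol 6.2)
- Radiotherapy: 6 weeks (SAP 5.1)
- End of radiotherapy to first MRI: 4 weeks (SAP 5.1, footnote l)
- First MRI to confirming MRI: 4 weeks (SAP 11.3.2)
- Total: 14 to 15 weeks (98 to 105 days). If the ±7-day MRI window of Protocol 6.2.2 is taken to apply to the first scan, the earliest time is about 13 weeks (91 days).

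**Accrual rate before the cut-off.** The documents give no count for the last weeks, so three rates are used, each assumed uniform.
- Planned: 400/365.25 = 1.095 per day.
- Observed average: 286 enrolled on 10 July 2019 (Protocol 1.1) and 616 on 28 April 2020, so 330/293 days = 1.126 per day. This assumes that the Protocol 1.1 sentence refers to the present trial. Its mention of 144 subjects in the MRZ arm and of a non-company sponsor supports that.
- Slower: the 749 − 616 = 133 later patients, over the 139 days to the IDMC meeting of 14 September 2020 taken as the end of recruitment, give 0.957 per day.

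**Patients too recent = rate × lag, as a share of 616.**

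| Lag | Planned | Observed | Slower |
|---|---|---|---|
| 13 weeks | 100 (16.2%) | 102 (16.6%) | 87 (14.1%) |
| 14 weeks | 107 (17.4%) | 110 (17.9%) | 94 (15.2%) |
| 15 weeks | 115 (18.7%) | 118 (19.2%) | 100 (16.3%) |

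**Effect on the rates.** If a share s is too recent, the expected ITT rate is (1 − s) × the rate among patients with enough follow-up. The relative shortfall is therefore s. As an illustration only, an assumed 20% would be reported as 0.20 × (1 − 0.192) = 16.2% to 0.20 × (1 − 0.141) = 17.2%.

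**Effect on the comparison.** With concurrent 1:1 randomisation, s is the same in both arms in expectation. For assumed rates of 20% against 30% and s = 0.18, the odds ratio moves from 1.71 to 1.66. With 308 per arm and one-sided 2.5%, power falls from 82% to 71%. Analysing only the older 82% of patients gives 74%, so the filter recovers little power.

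**Effect on interval coverage.** The table gives coverage of the assumed true rate by the exact interval at s = 0.19.

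| Assumed true ORR | 308 per arm | 154 per arm (half measurable, assumed) |
|---|---|---|
| 20% | 64% | 83% |
| 10% | 82% | 88% |
| 5% | 93% | 95% |

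At a true ORR of 20% with 308 per arm, coverage is 69% if s is 0.174. The documents state neither an expected ORR nor the share of patients with measurable disease.

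**The case against.** **No decision depends on it.** Response is one of the other secondary endpoints (SAP 5.2.2), analysed at exploratory significance (SAP 11.1), and the primary endpoint is OS. A reader might infer that the arm comparison is distorted. It is not: both arms are diluted alike, and the CMH test stays valid under the null. This objection stands and limits the point to the absolute rates.

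**The long-term analysis repairs it.** SAP 2 promises more mature data for all endpoints. That stands for the long-term report but does not help the primary report. Nor may the later rise be put down to this flaw alone, because best overall response accumulates until progression and later scans add real responses.

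**A 15-week filter is itself immature.** After the first scan, imaging is every 8 weeks. The second scan falls at about 18 to 19 weeks from randomisation and its confirmation at about 22 to 23. Patients between 15 and about 22 weeks have had one scheduled chance of a confirmed response. This stands, so the restricted rate cannot be presented as the final one.

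**The recent patients are not empty of information.** At the planned 16-month median (monthly hazard ln 2/16), about 7% of them would already have died and are known non-responders. At the observed rate that leaves about 103 to 110 still alive. It changes the count of patients not yet assessable. It does not remove the dilution, because the older group's rate already includes its own early deaths.

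**'Cannot' is too strong.** Protocol 7.1.1.3 allows earlier scans if clinically indicated. The statement holds for scheduled scans only.

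**The denominator is unsettled anyway.** Protocol 7.1.1 assesses objective response only in measurable disease, and SAP 11.3.2 does not repeat this. The objection stands, and the two questions should be settled together.

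**Conclusion.** The point holds for the absolute ORR and CR rates in the primary-analysis report. Roughly 14 to 19% of the 616 patients (about 107 to 118 at the planned or observed average accrual) were too recent for a confirmed response on scheduled scans. The per-arm rates are understated by up to about that relative share, measured against patients with time for a first confirmed response. This assumes uniform accrual before the cut-off and entry dates unrelated to response or measurability.

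Two stronger readings are not supported. One is that interval coverage falls to about 64%. That needs an assumed 20% ORR, all 308 patients per arm as denominator and a dilution near the top of the range. The other is that a third of patients are affected, since (110 + 133)/749 to (118 + 133)/749 is 32 to 34%. That puts patients randomised after the cut-off into an analysis fixed at the cut-off, which SAP 2 gives no ground for.

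**What to change.** In SAP 11.3.2, for the primary analysis:
- Keep the ITT analysis, and show 'not yet assessable at cut-off' as its own best-overall-response category with counts per arm.
- Add ORR and CR rates with exact intervals, the CMH test and the odds ratio in patients randomised at least 15 weeks (105 days) before the cut-off, that is on or before 14 January 2020.
- State that these restricted rates may still rise with later scans, and that the long-term follow-up analysis gives the mature rates.
- Reconcile the denominator with the measurable-disease limit in Protocol 7.1.1.

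The filter is a calendar date, so it depends on neither arm nor outcome. The cost is the wording, one filter, and a denominator in the added analysis smaller by about 16 to 19% (about 100 to 118 of 616 at the three accrual rates), with correspondingly wider intervals.
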